#### 6.6.3      **Safety endpoints**

**From CTP Section 7.5:** *For the safety data, including the primary endpoint, no missing data imputations are planned.*

The only exceptions where imputation might be necessary for safety evaluation are AE dates, and start and stop dates for concomitant medications. Missing or incomplete AE dates are imputed according to BI standards (see *KM Asset BI-KMED-BDS-HTG-0035 (3)*).

## **6.7            BASELINE, TIME WINDOWS AND CALCULATED VISITS**

For patients who are included directly into the maintenance period, measurements reported with date and time, and taken prior to start of administration of trial treatment are considered to be pre-treatment values. Measurements reported with a date only (and no time) and taken on the day of first administration of trial treatment are handled in a similar manner, i.e.

assigned as pre-treatment values. These pre-treatment values will be assigned to visits according to the nominal visit number as recorded on the eCRF or as provided by the laboratory.

For patients who are included directly into the re-induction period, measurements reported with date and time, and taken prior to start of administration of trial treatment are considered to be pre-treatment values. Measurements reported with a date only (and no time) and taken on the day of first administration of trial treatment are handled in a similar manner, i.e. assigned as pre-treatment values.

Baseline for derivation of the binary MCS efficacy endpoints, as well as for the efficacy endpoint displays over time are defined in [Section 5](#).

For safety endpoints, baseline for different treatment periods are defined in [Section 5](#).

Measurements taken after start of administration of trial treatment will be considered either on- or off-treatment values based on the definition in [Section 6.1](#), and will be assigned to visits for statistical analysis, if applicable, as defined below.

Analysis of AE data, concomitant medication or non-drug therapies, as well as use of rescue medication will not be based on visits. Therefore, no assignment to time windows will be necessary.

For derivation of the last value on treatment, minimum value on treatment, and maximum value on treatment, all on-treatment values (whether or not selected in any time window; see [Table 6.1: 1](#) and [Table 6.1: 4](#) for definition of the on-treatment period) will be considered; these will be derived for analysis of laboratory and vital signs data. For identification of potentially clinically significant abnormal laboratory values, all values (whether or not selected in any time window) within the on-treatment period will be considered.

Safety lab, vital sign, efficacy and biomarker measurements will be assigned to visits based on extended time windows around the planned visit dates, defined relative to the day of first re-induction, maintenance, or disease flare treatment depending on analysis phase. These extended time windows are defined below as well as their planned analyses.

- Re-induction period ([Table 6.7: 1](#)): efficacy, safety, and biomarker
- Overall maintenance treatment period ([Table 6.7: 2](#)): efficacy, safety, and biomarker
- Disease flare treatment period ([Table 6.7: 3](#)): efficacy, and safety

Table 6.7: 1 Time windows for assignment of efficacy, safety lab, vital signs and biomarker to visits for statistical analysis for re-induction period

Visit number /name	Visit label	Planned day	Time window (Days)				
			Window (per CTP)	Start (per CTP)	End (per CTP)	Start (extended)	End (extended)
V1	Screening/ R-baseline*	-7 to -2	n/a				
V1a	Screening	-2 to -1	n/a				
I1	RI-Week 0	Day 1	+/-0	1 A	1 A	≤1 A	1 A
Planned On-Treatment Data							
I2	RI-Week 4	Day 29	+/-3	26	32	2	43
I3	RI-Week 8	Day 57	+/-3	54	60	44	71
I4	RI-Week 12	Day 85	+/-3	82	88	72	99 B
All Data (planned Off-Treatment data)							
Unsche duled	Unscheduled					100	148
EOS C	Week 24/EoS	Day 170	[contact]	Day of last f-up value

Days are counted relative to the day of first i.v. treatment of re-induction period, which is defined as Day 1.

\* For derivation of binary MCS based efficacy endpoints, the baseline refers to baseline of parent trial. The R-baseline for efficacy endpoint displays over time refers to EoT of parent trial (V1 of current study).

A Note that measurements made at Day 1 and assigned to the on-treatment period (because mistakenly made after start of infusion of trial treatment) via assessment on date and time (i.e. safety laboratory) will not be assigned to Day 1. Such data will be listed only.

B All data after a patient has taken the first dose in the subsequent maintenance period are not applicable for reporting as a part of the re-induction period.

C EOS is only applicable to those patients who do not enrol into the maintenance period.

Table 6.7: 2 Time windows for assignment of efficacy, safety lab, vital sign and biomarker to visits for statistical analysis for overall maintenance treatment period

Visit number	Visit label /name	Planned day	Time window (Days)				
			Window (per CTP)	Start (per CTP)	End (per CTP)	Start (extended)	End (extended)
V1	Screening/ M-baseline*	-7 to -2	n/a				
V1a	Screening	-2 to -1	n/a				
M1	M-Week 0	Day 1	+/-0	1 A	1 A	≤1 A	1 A
Planned On-Treatment Data							
M2	M-Week 12	Day 85	+/-7	78	92	2	127
M3	M-Week 24	Day 169	+/-7	162	176	128	211
M4	M-Week 36	Day 253	+/-7	246	260	212	295
...	...	...	...	Planned date-7	Planned date+7	End of extended window of last visit+1	Midpoint of planned days between current visit and next visit
M29/E OT	M-Week 336/EoT	Day 2353	+/-7	2346	2360	End of extended window of last visit+1	Minimum of (2395, LD B +112)
All Data (planned Off-Treatment data)							
Unsche duled	Unscheduled					2396	2444
EOS	EoS	Day 2466	+7	2466	2473	Minimum of (2396, LD B +113)	Day of last f-up value

Days are counted relative to the day of first s.c. treatment in maintenance period, which is defined as Day 1 for maintenance.

\* For derivation of binary MCS efficacy endpoints, the baseline refers to baseline of parent trial. The M-baseline for efficacy endpoint displays over time refers to EoT of parent trial (V1 of current study) for initial responders and visit I4 (RI-Week 12) for responders after re-induction.

A Note that measurements made at Day 1 and assigned to the on-treatment period (because mistakenly made after start of injection of trial treatment) via assessment on date and time (i.e. safety laboratory) will not be assigned to Day 1. Such data will be listed only.

B LD = Day of last treatment received in the overall maintenance treatment period regardless of flare occurrence;

Table 6.7: 3 Time windows for assignment of efficacy, safety lab, and vital signs to visits for statistical analysis for disease flare treatment period

Visit number/name	Visit label	Planned day	Time window (Days)				
			Window (per CTP)	Start (per CTP)	End (per CTP)	Start (extended)	End (extended)
F0y Fx-Week 0	Fx-baseline*	-5 to -3	n/a				
	Fx-Week 0	1	+/-0	1 A	1 A	≤1 A	1 A
Planned On-Treatment Data							
Fx-Week 6	Fx-Week 6	Day 43	+/-7	36	50	2	64
Fx-Week 12	Fx-Week 12	Day 85	+/-7	78	92	65	99

Visit number/name: 'x' represents disease flare occurrence.

Days are counted relative to the day of each corresponding flare i.v. treatment, which is defined as Day 1 of disease flare treatment period.

\* For clinical response/remission assessment after disease flare treatment based on mayo score related calculation, the baseline refers to data from flare confirmation visit with endoscopy or regular maintenance visit with endoscopy before administration of each disease flare treatment.

A Note that measurements made at Day 1 and assigned to the on-treatment period (because mistakenly made after start of infusion of trial treatment) via assessment on date and time (i.e. safety laboratory) will not be assigned to Day 1. Such data will be listed only.

Repeated and unscheduled efficacy, safety and biomarker measurements will be handled similarly to scheduled measurements and will also be assigned to a time window depending upon the date of measurement.

Only one observation per time window will be selected for statistical analysis at a particular visit. Generally, the value which is closest to the protocol planned visit day will be selected. For composite endpoints based on MCS subscores, the date of PGA assessment will be used for time window assignment, and the PGA with the most complete components (RBS/SFS/mESS) at the same visit will be identified and then the closest will be selected. If the date of PGA assessment is missing, the date of endoscopy will be used instead for time window assignment and calculation of SFS and RBS, if available. If there are two observations which have the same difference in days to the planned day, the later value will be selected. If there are two observations on the same day, then [for vital signs per nominal time-point] the latest value (according to the date and time) will be selected, [for other endpoints] the worst value will be selected.

Assignment of efficacy observations to visits based on time windows will be based on the non-imputed (observed) data.

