Footnotes for all Flow Charts:

1. Visit V1 of this long-term extension study should be performed during the last visit (V6/EOT) of the preceding trial 1368-0005 Part 1 or 1368-0004. Assessments performed at last visit (V6/EOT) in the previous trial do not have to be repeated at visit 1 in this trial. Patients not eligible to take part in trial 1368-0017 shall complete follow-up visit 16 weeks after last dose given in trial 1368-0004 or 1368-0005 Part I.
2. Visit V1a can be performed via telephone. Main reason for this visit is to check eligibility based on sigmoidoscopy and patient diary results in order to plan the next visit.
3. Sigmoidoscopies have to be performed every 48 weeks during maintenance treatment period. Additional sigmoidoscopies are to be done: a) at screening (EOT of previous trial); b) at W12 of re-induction period to check response to i.v. re-induction ([Flowchart 2](#)); c) In case of disease flare, an unscheduled confirmatory sigmoidoscopy has to be performed, followed in 12 weeks after i.v. re-induction to check response to disease flare treatment. Two sets of mucosal biopsies will be taken; 1 set for gene expression analyses and 1 set for histopathology/IHC analyses at each visit indicated. Sigmoidoscopy images will be centrally read by an external independent assessor(s); management of images will be performed by an external vendor. Colonoscopy instead of sigmoidoscopy can be performed if required as colon cancer screening per local guidelines.
4. Physical examination: C=complete, T=targeted. Refer to [Section 5.2.1](#) and [5.2.2](#). Measurement of vital signs should precede blood sampling and be assessed pre-dose at all dosing visits and at screening. In addition, at visits with s.c. study drug administration, vital signs will be assessed at approx. 10 minutes after study drug administration. At visits with i.v. study drug administration, vital signs will be assessed at approximately 5 and 60 minutes after study drug administration. Monitor for signs and symptoms of hypersensitivity reactions for 1h following i.v. study drug administration.

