13. For patients who discontinue study medication before scheduled end of treatment, an early EOT visit has to be scheduled. subsequently EOS visit 16 weeks after last dose of study medication has to be performed.
14. At visit R4 patient response status to i.v. re-induction has to be checked. Sigmoidoscopy and eDiary data review are part of eligibility check to continue into maintenance treatment. Patients who did not respond to i.v. re-induction will be discontinued from study medication and early EOT visit has to be performed. EOS visit has to be performed 16 weeks after last dose of study medication (16 weeks after R3 visit). Sigmoidoscopy does not need to be done at EOT visit for these patients.
15. Visit M1 ([flowchart](#) for re-induction non-responders) has to be performed after results of sigmoidoscopy performed at visit R4 are received (usually 5-7 days)
16. For patients with disease flares only, sigmoidoscopy does not need to be repeated if done within 6 weeks prior to EOT visit.
17. Patients who develop a disease flare during maintenance study treatment period confirmed by sigmoidoscopy will receive a single infusion of 1200mg BI 655130 (SPESOLIMAB) i.v. followed 6 weeks later by intensified maintenance treatment with 600mg BI 655130 s.c. q6w until the originally scheduled EOT visit (i.e. at week 336 after start of first sc. maintenance treatment)
18. Cycle of visits F1-x to F4-x (visits every 6 weeks) is repeated until originally scheduled EOT, 336 weeks after initial visit M1, is reached.
19. QuantiFERON-TB test should be done every 48 wks.

TABLE OF CONTENTS

TITLE PAGE	1
CLINICAL TRIAL PROTOCOL SYNOPSIS	2
FLOW CHART 1A: INDUCTION RESPONDERS V1, V1A, M1-M5B	4
FLOW CHART 1B: INDUCTION RESPONDERS M6-EOS.....	5
FLOW CHART 2: INDUCTION NON-RESPONDERS	6
FLOW CHART 3: PATIENTS WITH DISEASE FLARE.....	7
TABLE OF CONTENTS	10
ABBREVIATIONS	14
1. INTRODUCTION.....	18
1.1 MEDICAL BACKGROUND	18
1.2 DRUG PROFILE	18
1.3 RATIONALE FOR PERFORMING THE TRIAL	20
1.4 BENEFIT - RISK ASSESSMENT.....	21
2. TRIAL OBJECTIVES AND ENDPOINTS.....	34
2.1 MAIN OBJECTIVES, PRIMARY AND SECONDARY ENDPOINTS.....	34
2.1.1 Main objectives.....	35
2.1.2 Primary endpoint(s).....	36
2.1.3 Secondary endpoint.....	36
2.2 Secondary endpoints.....	36
2.3 Other endpoints.....	36
3. DESCRIPTION OF DESIGN AND TRIAL POPULATION	38
3.1 OVERALL TRIAL DESIGN AND PLAN	38
3.2 DISCUSSION OF TRIAL DESIGN, INCLUDING THE CHOICE OF CONTROL GROUP(S)	41
3.3 SELECTION OF TRIAL POPULATION	42

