Description of change	Recommended tapering schedule for oral corticosteroids (other than budesonide):

Proprietary confidential information © 2022 Boehringer Ingelheim International GmbH or one or more of its affiliated companies

	
Changed to: Recommended tapering schedule for systemic corticosteroids:

Rationale for change	Typo
Section to be changed	Section 10.7 Steroid tapering scheme
Description of change	
Recommended tapering schedule for oral budesonide MMX
 
Changed to:
 
Recommended tapering schedule for oral corticosteroids with limited systemic bioavailability
 
Added sentence:
 
Patients on stable dose of beclomethasone dipropionate will be requested to stop using it after they achieve clinical response or clinical remission.

Rationale for change	Added for clarification

11.2 GLOBAL AMENDMENT 2

Date of amendment	6 Nov 2018
EudraCT number	2018-000334-35
EU number	
BI Trial number	1368-0017
BI Investigational Product(s)	BI 655130
Title of protocol	An open label, long term safety trial of BI 655130 treatment in patients with moderate to severely active ulcerative colitis who have completed previous BI 655130 trials
To be implemented only after approval of the IRB / IEC / Competent Authorities	
To be implemented immediately in order to eliminate hazard – IRB / IEC / Competent Authority to be notified of change with request for approval	
Can be implemented without IRB / IEC / Competent Authority approval as changes involve logistical or administrative aspects only	
Section to be changed	Protocol Synopsis, Main Inclusion and Exclusion Criteria
Description of change	Men able to father a child removed
Rationale for change	Reflecting updated IB ver.5.0
Section to be changed	Flowchart 2
Description of change	Coding to visits R1, R2, R3 and R4 added I01, I02, I03 and I04 respectively
Rationale for change	To be in line with internal and external databases
Section to be changed	Flowchart 3
Description of change	Sigmoidoscopy note – updated from : first sigmoidoscopy 12 weeks from Flare confirmation (F0y) to - first sigmoidoscopy 12 weeks from i.v. re-induction (R0y), then every 48 weeks from R0y
Rationale for change	Mistakenly entered in previous version
Section to be changed	Flowchart 3
Description of change	Diary review requirement added at visit F0y
Rationale for change	Forgotten to be ticked in previous version

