Rationale for change	
Amongst the first 24 patients who responded to the induction treatment in the previous trials and rolled over to trial 1368.17, more than 50% have experienced a relapse/flare during the first 6 months after switch from the induction to the maintenance dose. This rate is higher compared to the one observed with approved drugs for the same condition.
 
The switch from the higher spesolimab induction doses (450 mg q4w i.v. for 12 weeks and 1200 mg q4w i.v. for 12 weeks) in the previous trials to the current maintenance dose in trial 1368.17 (300 mg q12w s.c.) represent a reduction in exposure by a factor of 6.4 and 17.1 respectively (given a 70% bioavailability of the s.c. vs the i.v. dose) during a 12 week period. The observed drop in efficacy may thus be explained by a decrease of drug exposure below the threshold required to maintain maximum target engagement. The individual 300mg SC dose corresponds to ~210mg IV dose, which for an average 70kg person represents the lowest dose of $\geq 3\text{mg/kg}$ achieving maximal target engagement, though target engagement in HV was quite sustainable for more than 10 weeks (see IB section 6). However, in UC patients a higher clearance rates of biologics and the need for target engagement in the gut tissue may require higher dosing than HV. Therefore, after one half-life of about 4 weeks (or shorter), patients may have developed insufficient drug exposure to maintain full target engagement in the gut, while q4w dosing may maintain drug exposure in the therapeutic range.
 
Since for study logistics reasons the SC injection interval in the intensified maintenance treatment cannot be reduced to q4w, a higher dose of 600mg will be applied to double the exposure compared to the original regimen.
 
Even assuming a negative spesolimab efficacy on ulcerative colitis, the proposed dose change, is considered not harmful for the patients, since it is lower than the doses previously tested in healthy

Proprietary confidential information © 2022 Boehringer Ingelheim International GmbH or one or more of its affiliated companies

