### 6.6.2      **Efficacy endpoints**

**From CTP Section 7.5:** *With regards to the handling of missing data on those efficacy outcomes derived from the MCS, no missing data imputations are planned to be performed.*

In order to appropriately handle missing data in this trial, it is first necessary to define which are the inter-current events within each trial part, that lead to specific decisions being made upon the respective efficacy endpoint outcome, with such decisions being dependent upon the occurrence and timing of these events.

Any occurrence of the following will represent an inter-current event during both the re-induction and maintenance trial parts:

- Intake of rescue medication (as defined in [section 5.4.4](#)).  
Data after occurrence of such an event will be censored, and, handled subsequently according to the applicable missing data strategy described below.

In addition, any occurrence of the following will represent an inter-current event during the maintenance trial part:

- Occurrence of a confirmed disease flare (as defined in [Section 5.4.6](#)), or the intake of a dose of disease flare medication with 1200 mg BI 655130 SD.

Data after occurrence of such an event will be included in displays of the efficacy endpoints since treatment with spesolimab i.v. (to treat a disease flare) is not considered to represent a failed treatment outcome in this trial.

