#### Efficacy imputation rules

The following rules apply for all treatment periods with defined efficacy endpoints. Missing data imputation, when performed, will not be done for missing assessments due to implementation of any cut-off date.

The following imputation strategy will be applied to the reporting of continuous efficacy data.

- Observed cases (OC) approach: prior to observing the applicable efficacy endpoint, data will be reported with no imputation performed on the missing data irrespective of whether the data is considered to be randomly missing, or missing due to prior occurrence of an applicable intercurrent event.

The following imputation strategy will be important for the display of binary efficacy data:

- No Response Imputation [NRI]: prior to observing the applicable binary efficacy endpoint, all missing data will be set to non-response irrespective of whether the data is considered to be randomly missing, or missing due to prior occurrence of an applicable intercurrent event. Only patients continuing at this visit per time window before interim cut-off will be included in the denominator.

The following imputation strategy will be important for the display of, i.e. safety laboratory data:

- Observed cases including values after any use of rescue medication (OC-IR): this approach is an extension of the OC approach which includes all values which were measured both before and after any rescue medication intake. The analysis using the OC-IR approach is then only based on the patients with observed data.

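### If endoscopies after a flare run from the flare infusion, the SAP's windows (counted from the first maintenance dose) and NRI score most continuing flare patients as non-remitters at weeks 48 to 288 by schedule alone

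*SAP*

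**What the plan says.** **Windows.** SAP 6.7, Table 6.7:2, sets 12-weekly visits for the overall maintenance period, with limits midway between planned days. The origin is fixed: "Days are counted relative to the day of first s.c. treatment in maintenance period, which is defined as Day 1 for maintenance". Nothing resets it after a flare. Table 6.7:3 has a flare clock, but it stops at week 12 after the infusion.

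**Missing data.** SAP 6.6.2 keeps post-flare efficacy data because "treatment with spesolimab i.v. (to treat a disease flare) is not considered to represent a failed treatment outcome in this trial". For binary endpoints, "all missing data will be set to non-response irrespective of whether the data is considered to be randomly missing". The denominator is limited to patients continuing at the visit. Clinical remission needs mESS (Protocol Table 2.1:1), and one missing subscore makes the outcome missing (Protocol 7.5).

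**Endoscopy schedule.** Protocol flow-chart footnote 3 says "Sigmoidoscopies have to be performed every 48 weeks during maintenance treatment period". In case of a flare, "an unscheduled confirmatory sigmoidoscopy has to be performed, followed in 12 weeks after i.v. re-induction". The log of Amendment 2 records the wording introduced into Flow Chart 3: "first sigmoidoscopy 12 weeks from i.v. re-induction (R0y), then every 48 weeks from R0y". R0y is the flare infusion visit.

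**End of treatment.** Footnotes 17 and 18 keep EOT at week 336 from the first maintenance visit (M1). Footnote 16 adds: "For patients with disease flares only, sigmoidoscopy does not need to be repeated if done within 6 weeks prior to EOT visit".

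**The concern.** A patient with no flare has annual endoscopies in the middle of the week-48, 96, ... windows. A patient whose 48-week cycle restarts at the flare infusion usually does not. That patient can attend every required endoscopy, be in remission at each one, and still have no mESS in the window. NRI then records non-remission.

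The failure would reflect the date of the flare, not the state of the disease. Flare patients who do not respond within 12 weeks, or who have a second confirmed flare, are withdrawn (Protocol 3.3.4.1). Those still in the denominator are therefore largely responders to flare treatment, the group whose later remission the retained data should show. Several interim analyses are planned over seven years, so intermediate visits are likely to be read.

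**Working it through.** **1. Reproduce the SAP windows.** Planned day = 7 × week + 1, and window end = midpoint of adjacent planned days.
- M2: (85 + 169)/2 = 127. M3: (169 + 253)/2 = 211. M4: (253 + 337)/2 = 295. M29: 2353 + 42 = 2395. All four match Table 6.7:2.
- The window for week 48k therefore runs from day 336k − 40 to day 336k + 43: days 296-379 (week 48), 632-715 (week 96), up to 1976-2059 (week 288).

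**2. Post-flare endoscopies on the R0y clock.** For an infusion on maintenance day f, they fall on f + 84 and then f + 336, f + 672, and so on.

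**3. Infusion days that put an endoscopy in the week-48 window (infusion before it opens).**
- f + 336 lies in 296-379 when f ≤ 43.
- f + 84 lies in 296-379 when f is 212-295.
- Infusion on days 44-211 (168 days) gives none.

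**4. Later windows, infusion on days 1-336.** Covered days are 1-43 and 296-336, which is 43 + 41 = 84. The share covered is 84/336 = 25%, so 75% are not. An infusion on any of days 44-211 leaves all six windows from week 48 to week 288 empty.

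**5. Share without a scheduled endoscopy.** The documents give no distribution of flare times, so each range assumes uniform timing.

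| Assumed infusion days | Window | Not covered |
|---|---|---|
| 1-295 | week 48 | 168/295 = 57% |
| 29-295 | week 48 | 168/267 = 63% |
| 1-336 | weeks 96-288 | 252/336 = 75% |
| 1-182 | weeks 48-288 | 139/182 = 76% |
| 29-182 | weeks 48-288 | 139/154 = 90% |

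If infusions up to day 336 are included and the confirmatory endoscopy is counted (taken as 4 days before infusion), the week-48 figure falls to (168 + 4)/336 = 51%. The extra covered patients are those flaring inside the window.

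**6. Example.** An infusion at week 20 (day 141) gives endoscopies at weeks 32, 68, 116, 164, 212, 260 and 308. None lies in an annual window from week 48 to week 288.

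**7. Other anchors.** If the 48-week cycle ran from the first s.c. dose after the flare (f + 42), no infusion on days 29-182 would be covered. If it stayed on the M1 clock, every window would be covered.

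**8. Week 336.** M28 is planned for day 2269 and M29 for day 2353. The midpoint is 2311, so the week-336 window opens on day 2312. Footnote 16 allows 42 days:
- EOT on day 2353: from day 2311, 1 day outside.
- EOT on day 2346: from day 2304, 8 days outside.
- EOT on day 2360: from day 2318, none outside.

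An excused endoscopy on days 2304-2311 falls in the week-324 window.

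**The case against.** The strongest objection is that the R0y clock appears only in an amendment log. Flow Chart 3 was amended again later and is not reproduced. Footnote 3 gives no anchor for the 48-weekly endoscopies and lists the flare ones as extra. Protocol 6.1 counts every visit up to EOT from Day 1. On that reading the annual endoscopies stay on the M1 clock and the windows fit.

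This stands as a reason to make the finding conditional. It does not remove it. The log gives the R0y wording as the text brought in, and no visible later entry withdraws it. Footnote 10 speaks of a flare patient's counterpart of week 144. Protocol 4.1.4 counts rescheduled visits in flare patients from the first s.c. dose after the flare. These places must be reconciled.

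A reader might take footnote 16 as proof of an off-schedule clock. It is not: with annual endoscopies on the M1 clock, the 12-week post-flare endoscopy could still fall in the six weeks before EOT.

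It is also fair that no annual remission endpoint is visible. The SAP's further-endpoint sections are not in the available text, and the only remission endpoint seen is at week 336. Use of NRI at intermediate visits is inferred from the SAP's general rule for binary efficacy data. Maintained remission in Protocol Table 2.1:1 already excludes patients with a flare. The trial is descriptive, and individual values will be listed.

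**Conclusion.** The point holds conditionally. If Flow Chart 3 still uses the R0y clock, about 57-90% of continuing flare patients infused before a given week 48-288 window opens have no scheduled endoscopy in it, and about 75% once the flare clock is established. Any mESS-based annual display would score them as non-remitters by schedule, contrary to SAP 6.6.2. The range rests on uniform flare timing over assumed intervals and on visits kept to plan.

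Two stronger readings are tempting, and the documents do not support them.
- **A bias in percentage points.** A reader might multiply the amendment rationale's figure, "more than 50% have experienced a relapse/flare during the first 6 months after switch", by the uncovered share and a guessed remission rate. That figure covers 24 responders under the former q12w dosing and flare definition. The documents give no remission rate for continuing flare patients. NRI also counts only patients continuing at the visit, so the share of all starters is the wrong base. Some uncovered patients would be non-remitters anyway.
- **A compromised secondary endpoint.** EOT stays on the M1 clock and an endoscopy is due there unless excused. Only an excused endoscopy 1 to 8 days before day 2312 is lost. For one on or after day 2312, SAP 6.7 prefers the PGA visit with the most complete components and can select it.

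**What to change.** 1. **Anchor.** State in the SAP which clock governs 48-weekly endoscopies after a flare, once Flow Chart 3, footnote 3 and Protocol 4.1.4 and 6.1 have been reconciled.
2. **NRI (SAP 6.6.2 and 6.7).** For outcomes that need mESS, apply NRI at a visit only if an endoscopy was due in that window under the patient's own schedule, including when it was due and missed. Show observed cases alongside, with the actual endoscopy week. This display would also match Protocol 7.5, which plans no imputation for Mayo-based outcomes.
3. **Week 336.** State that an endoscopy excused under footnote 16 counts as the EOT mESS even if dated before day 2312. The rule must be explicit, because SAP 6.7 assigns composites by PGA date and takes components from the same visit.

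The cost is SAP wording and programming, with no new procedures. The downside is smaller denominators for flare patients at intermediate annual visits, so those proportions would lean towards patients without a flare. Report how many continuing flare patients had no endoscopy due. Windows 48 weeks wide are an alternative, but they can hold two endoscopies: days 225 and 477 both lie within 337 ± 168 for the week-20 flare. They can also report a result from up to 24 weeks away.
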